5. Two follow-up (FU) Visits are planned. FU1 (V29) must take place 7-12 days after the actual date Visit 28 is performed. FU 2 (P30) should take place 30 days after Visit 28.
6. 2-point profiles (SMPG): pre-breakfast and pre-dinner (main evening meal) SMPGs should be taken throughout the trial for titration/dose adjustments. Please see appendix A for details.
7. 9-point profiles (SMPG) must be started in the morning 2 days before Visits 2, 14, 18 and 28. Measurements are to be performed before and after (90 min after the start of the meal) breakfast, lunch, main evening meal, before bedtime, at 4 am and before breakfast on the following day. Please note that the 9-point profile (SMPG) is overlapping with the 2-point profile (SMPG).
8. Pregnancy test: At Visits 1 and 28 a blood pregnancy test will be performed in women of child bearing potential. During the trial a urine pregnancy test will be performed if a menstrual period is missed or pregnancy is suspected. If at phone contacts, subjects report missed menstrual period, the subject will have to attend the site for a urine pregnancy test.
9. The baseline ECG should be performed between the screening Visit 1 and the randomisation Visit 2, and results must be available before randomisation. The end of treatment ECG should be performed at Visit 28.
10. A funduscopy or fundus photography performed for any reason unrelated to this trial within 12 weeks prior to screening visit (Visit 1) is acceptable provided no clinical symptoms suggestive of eye disease have occurred in the meantime. It is allowed to perform the Visit 1 funduscopy or fundus photography between Visit 1 and Visit 2. The results must be available prior to randomisation. Funduscopy/fundus photography performed within a period of three weeks before Visit 28 is acceptable if results are available at the visit and provided no clinical symptoms suggestive of eye disease have occurred in the meantime.

11. PRO questionnaires; A battery of PRO questionnaires will evaluate health related quality of life, treatment satisfaction and preferences. The PRO questionnaires should be filled in by the subject at the visits preferably after conclusion of all fasting related activities, but before any other trial related procedures.
12. At baseline (Visit 2) only SF-36 & TRIM-D will be completed by subjects. At visit 14 & visit 28 all PROs (SF-36, TRIM-D, TRIM-D Device, and Device Specific Questionnaires (DSQ) I & II will be filled in.

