## 8.4 Diaries

All subjects will be provided with diaries. The subject's diaries will be collected after each site visit and will be kept at the trial site as source documents.

The subjects will be instructed in recording the following in the diary:

- date and value of all 2-point profile (SMPG) measurements (V3-V28)
- date, actual clock time (hh:mm) and value of all 9-point profile (SMPG) measurements (V2, V14, V18 and V28)
- dates and doses of IDegAsp 30 or BIAsp 30, on three days before Visit (V3-V28)
- date, time point and dose of first doses of trial product (IDegAsp 30 or BIAsp 30) (V3)
- date, time point and dose of last dose of trial product (IDegAsp 30 or BIAsp 30) (V28)
- date, dose and time point (breakfast/ main evening meal) of the BHI 30 injection on the first day (V28), 2 days and 4 days after Visit 28 and on the last day before FU1 (V29) hypoglycaemic episodes V2-V29
- medical problems (V2-P30)
- changes in concomitant medication (including changes in doses of metformin if any) (V3-V29)

The above data will be transcribed into the eCRF by the investigator.

The investigator is allowed to record the following in the diary:

- prescribed doses of trial insulin
- time and date of next visit and/or phone contact
- subject ID and site contact details

Diaries must be reviewed by the investigator to ensure that AEs, including any overall change in health and concomitant medication, are reported. The review must be documented on the front page of the diary and data must be transcribed into the eCRF.

If clarification of entries or discrepancies in the diary is needed, the subject should be questioned and a conclusion made in the medical record. Care should be taken not to bias the subject.

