**Table 8–1 Timepoints for 9-point profile (SMPG)**

Timepoint	2 Days before visit	1 Day before visit
Before breakfast	✓	✓
90 min after the start of breakfast	✓	
Before lunch	✓	
90 min after the start of lunch	✓	
Before main evening meal	✓	
90 min after the start of main evening meal	✓	
Before bedtime	✓	
At 4 am	✓	

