### ***2-point profile (SMPG) values used for dose adjustment***

The endpoints from the SMPG measurements obtained throughout the trial for dose adjustment will be:

- Mean PG before meals (breakfast and main evening meal) after 26 weeks of treatment
- Responder for PG titration targets
- Time from randomisation (measured in weeks) to achieve titration targets
- Within-subject variability as measured by CV% after 26 weeks of treatment

The mean PG value before a meal will be calculated at each visit using the available data and separately for breakfast and main evening meal.

The mean before meal PG values after 26 weeks of treatment will be analysed separately, using an ANOVA method with treatment, anti-diabetic therapy at screening and sex as fixed factors, and age and the corresponding mean PG value at baseline as covariates.

From the mean before meal PG value, a dichotomous endpoint (responder/non-responder) will be derived for each meal that shows if a subject has achieved the titration target at each visit.

For each target a survival endpoint will be derived as the time from randomisation to the date a subject achieves the titration target for the first time.

The two survival endpoints will be analysed separately in a Cox proportional hazards model including treatment, anti-diabetic therapy at screening and sex as fixed factors and age as covariate. An analysis will also be performed for the time to all titration targets are met. Subjects that are lost for follow up without meeting the target and subjects that never meet the target during treatment will be censored at the last day of treatment.

The logarithm transformed SMPG values available before breakfast and main evening meal, will be analysed separately as repeated measures in a linear mixed model with treatment, anti-diabetic therapy at screening and sex as fixed factors, age as covariate and subject as random factor. The model will assume independent within- and between-subject errors with variances depending on treatment. Within-subject variability as measured by CV% for a treatment can be calculated from the corresponding residual variance  $\sigma^2$  as  $CV\% = 100\sqrt{(\exp(\sigma^2)-1)}$ . The confidence interval for the CV ratio between treatments will be calculated using the delta method.

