A mixed effect model will be fitted to the 9-point profile (SMPG) data. The model will include treatment, time, interaction between treatment and time, anti-diabetic therapy at screening and sex as fixed factors, age and the values from the profile at baseline as covariates and subject as random effect. From the model, mean profile by treatment and relevant treatment differences will be estimated and explored.

Mean and fluctuation in the 9-point profile (SMPG) and prandial PG increment endpoints will be analysed separately using an ANOVA method with treatment, anti-diabetic therapy at screening and sex as fixed factors, and age and the relevant baseline value as covariates. Fluctuation in the 9-point profile (SMPG) will be logarithm transformed before analysed.

2-point profile (SMPG) values used for dose adjustment

The endpoints from the SMPG measurements obtained throughout the trial for dose adjustment will be:

- Mean PG before meals (breakfast and main evening meal) after 26 weeks of treatment
- Responder for PG titration targets
- Time from randomisation (measured in weeks) to achieve titration targets
- Within-subject variability as measured by CV% after 26 weeks of treatment

The mean PG value before a meal will be calculated at each visit using the available data and separately for breakfast and main evening meal.

The mean before meal PG values after 26 weeks of treatment will be analysed separately, using an ANOVA method with treatment, anti-diabetic therapy at screening and sex as fixed factors, and age as covariates.

From the mean before meal PG value, a dichotomous endpoint (responder/non-responder) will be derived for each meal that shows if a subject has achieved the titration target at each visit.

For each target a survival endpoint will be derived as the time from randomisation to the date a subject achieves the titration target for the first time.

The two survival endpoints will be analysed separately in a Cox proportional hazards model including treatment, anti-diabetic therapy at screening and sex as fixed factors and age as covariate. An analysis will also be performed for the time to all titration targets are met. Subjects that are lost

for follow up without meeting the target and subjects that never meet the target during treatment will be censored at the last day of treatment.

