2.6 Health economics and/or patient reported outcomes

The following questionnaires will be used to compare PROs and costs associated with hypoglycaemia between treatments:

- SF-36^{4,5}
- TRIM-D⁶ and TRIM-D Device⁶
- Device Specific Questionnaires I and II⁷

For the questionnaires , SF-36 and TRIM-D the change in score (total score if appropriate) from baseline will be analysed separately using an ANOVA method with treatment, anti-diabetic therapy at screening and sex as fixed factors, and age and the relevant baseline value as covariates.

For the device questionnaire TRIM-D Device , which is not assessed at baseline, the score (total score if appropriate) will be analysed using an ANOVA method with treatment, anti-diabetic therapy at screening and sex as fixed factors, and age as covariate.

For Device Specific Questionnaires I and II, since there are no validated scoring algorithms, formal statistical analysis will not be conducted and only descriptive statistics will be presented.

3 Changes to the statistical analyses planned in the protocol

There were 2 minor changes to the statistical analyses planned in the protocol as described below:

- The mean PG at baseline as covariate in the analysis for the 2-point SMPG profiles was not included since the 2-point SMPG was not collected until visit 3.
- Last Observed Value (LOV) was defined to summarise efficacy data and replace LOCF in summary table.

4 References

1. EMEA-Committee for Proprietary Medicinal Products. CPMP/EWP/482/99 - Points to consider on switching between superiority and non-inferiority. 27-2-2000.
2. Food and Drug Administration. Food and Drug Administration, Code of Federal Regulations, Guidance for Industry, Diabetes Mellitus: Developing Drugs and Therapeutic Biologics for Treatment and Prevention. Draft Guidance. 2008.
3. Rubin DB. Inference and missing data. *Biometrika* 1976; 63(3):581-592.
4. Ware JE, Jr., Sherbourne CD. The MOS 36-item short-form health survey (SF-36). I. Conceptual framework and item selection. *Med Care* 1992; 30(6):473-483.

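### The SAP drops the baseline covariate for week-26 pre-meal glucose, although the Visit 2 nine-point profile supplies a usable proxy

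*SAP*

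**What the plan says.** Protocol section 17.4.2.1 analyses mean plasma glucose before breakfast and before the main evening meal at week 26, each in its own ANOVA. The covariates are "age and the corresponding mean PG value at baseline as covariates".

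The SAP keeps the endpoint but not the baseline term. Section 2.4.2.1 gives the model as treatment, "anti-diabetic therapy at screening and sex as fixed factors, and age as covariates". The change is announced in SAP section 1.2 and logged in section 3, where the baseline mean "was not included since the 2-point SMPG was not collected until visit 3".

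For the nine-point profile, the same SAP section 2.4.2.1 does adjust for baseline. Its mixed model takes "age and the values from the profile at baseline as covariates and subject as random effect", and the ANOVAs of the profile mean, the fluctuation and the prandial increments each take the relevant baseline value.

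**The concern.** The stated reason shows that no 2-point baseline exists. It does not show that no baseline glucose exists at these two meal times. If pre-randomisation readings at the same times are on file, the endpoint loses an adjustment the protocol intended although a substitute is available.

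The stake is limited to the width of one confidence interval per meal and the exposure of each estimate to chance imbalance at baseline. SAP section 2 treats endpoints of this kind as supportive and presents no p-values for them.

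**Working it through.** **What is collected, and when**

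- 2-point series: the diary (protocol 8.4) lists "date and value of all 2-point profile (SMPG) measurements (V3-V28"), so there is no 2-point value at baseline and the SAP's reason is correct as far as it goes.
- Nine-point series: the same diary lists "date, actual clock time (hh:mm) and value of all 9-point profile (SMPG) measurements (V2, V14, V18 and V28"). Flow chart footnote 7 says "9-point profiles (SMPG) must be started in the morning 2 days before Visits 2, 14, 18 and 28".
- Content of one profile (protocol Table 8-1): pre-breakfast on two consecutive days and pre-main-evening-meal once. The profile ends on the morning before Visit 2, so every reading precedes randomisation. Under section 8.1.1, subjects are still on their pre-trial treatment.
- Equipment: the glucose meter is handed out at Visit 1 (section 8.6.9).

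The Visit 2 profile therefore gives two readings for breakfast and one for the evening meal. The 2-point endpoint averages up to three readings per meal (section 8.6.9.1).

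**Group sizes**

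The plan gives no figure for this endpoint. I use the planned 358 and 179 from protocol Table 17-3. Those follow from 456 / (1 - 0.15) = 536.5, raised to 537 and split 2:1.

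**Precision and chance imbalance**

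Let rho be the partial correlation between the covariate actually entered and the week-26 outcome, given prior therapy, sex and age. It is an assumption; the documents give none.

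- CI width, adjusted relative to unadjusted: sqrt(1 - rho²).
- SE of the baseline difference between arms: sqrt(1/358 + 1/179) = 0.0915 SD. The 95% limit for a chance difference is 1.96 × 0.0915 = 0.179 SD.
- Shift left in the unadjusted estimate at that limit: rho × 0.179 SD.

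| Assumed rho | CI width multiplier | Shift (SD) |
|---|---|---|
| 0.1 | 0.995 | 0.018 |
| 0.2 | 0.980 | 0.036 |
| 0.3 | 0.954 | 0.054 |
| 0.4 | 0.917 | 0.072 |
| 0.5 | 0.866 | 0.090 |

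**How much a proxy loses**

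With day-to-day intraclass correlation ICC (also assumed), the reliability of k readings is R_k = k·ICC / (1 + (k - 1)·ICC). Relative to a three-reading mean, k readings keep the share sqrt(R_k / R_3) of the correlation.

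| Assumed ICC | One evening reading | Two breakfast readings |
|---|---|---|
| 0.3 | 73% | 91% |
| 0.5 | 82% | 94% |
| 0.7 | 89% | 97% |

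As an example, suppose a three-reading baseline would have had rho 0.1, 0.2 or 0.3 and ICC is 0.5. The single evening reading then gives sqrt(1 - (0.816·rho)²) = 0.997, 0.987 or 0.970.

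**Missing Visit 2 values**

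With a fraction m missing, mean imputation gives the multiplier sqrt(1 - rho²(1 - m)), and dropping those subjects gives sqrt((1 - rho²)/(1 - m)). At an assumed m = 0.1:

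| Assumed rho | Mean imputation | Complete case |
|---|---|---|
| 0.1 | 0.996 | 1.049 |
| 0.2 | 0.982 | 1.033 |
| 0.3 | 0.959 | 1.006 |

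A simulation of 4,000 trials per value of rho gave 0.996, 0.983 and 0.960 against 1.050, 1.034 and 1.007, with no bias in the treatment estimate.

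**The case against.** The strongest reply is that the SAP makes no error. The protocol's covariate cannot be formed from the 2-point series. The SAP noticed this, disclosed the change and gave a true reason. Using a substitute is a choice among valid analyses. That stands, and it is why the point is an optional improvement.

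A second reply is that the adjusted picture is already in the plan. If measurements are made as scheduled, two of the three pre-breakfast readings and one of the three pre-evening-meal readings behind the week-26 means also belong to the Visit 28 nine-point profile, whose model adjusts for baseline. Baseline-adjusted fasting plasma glucose is also a confirmatory endpoint. This limits the loss but does not remove it: the nine-point model works on individual readings, and the three-reading mean is a separately listed endpoint.

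Third, the gain may be small. Titration to a common target weakens the link with baseline, and the single evening reading is noisy. This is fair. Proxy noise moves rho down within the range shown, and at the low end the gain is under 1% of CI width.

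Fourth, the missing-value rule would apply to this ANOVA alone, and Visit 2 laboratory glucose is another candidate baseline for breakfast. Both are true. The profile readings are preferred because they come from the same meter at the same meal times and cover both meals.

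**Conclusion.** The point holds, as an optional improvement. The SAP's reason is true of the 2-point series, but a proxy baseline for both meals is scheduled for collection before randomisation and is already used elsewhere in the SAP. Only the 2-point mean endpoint is left without the adjustment the protocol planned.

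The cost is a CI that adjustment would narrow by about 0.5% to 13% for rho between 0.1 and 0.5, with the lower part of that range plausible, and an uncorrected shift of up to 0.018 to 0.090 SD if baseline imbalance reaches its 95% limit. These figures rest on assumed correlations and the planned group sizes. Because treatment is randomised there is no systematic bias, and the primary analysis and the testing hierarchy are unaffected.

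**What to change.** For the ANOVA of week-26 mean pre-meal glucose only, add a baseline covariate from the Visit 2 nine-point profile:

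- **Pre-breakfast endpoint:** the mean of the two pre-breakfast values.
- **Pre-main-evening-meal endpoint:** the single value before that meal.
- **Missing Visit 2 value:** replace it by the overall mean pooled across both arms, so that no subject is lost. Without this rule, 10% missing values would make the CI wider than with no adjustment at rho 0.1 to 0.3.
- **SAP section 3:** state that the covariate is a proxy for the protocol's baseline mean. If the sponsor prefers not to use it, say there why the Visit 2 readings were judged unsuitable.

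The cost is two SAP sentences, a small programming change and one degree of freedom per model. No new data are needed.
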